Describe the plan to be followed by the principal investigator/study staff to monitor and assure the validity and integrity of the data and adherence to the IRB-approved protocol. Specify who will be responsible for monitoring, and the planned frequency of monitoring. For example, specify who will review the accuracy and completeness of case report form entries, source documents, and informed consent.

NOTE: Regardless of monitoring plans by the sponsor or others, the principal investigator is ultimately responsible for ensuring that the study is conducted at his/her investigative site in accordance with the IRB-approved protocol, and applicable regulations and requirements of the IRB.

[name] will be present during the consent procedure, and all data collection periods. This will ensure that the study protocol is followed, and quality data are obtained. All data will be reviewed at a bi-annual meeting of the co-investigators.

For guidance, refer to the following Partners policies:

Data and Safety Monitoring Plans and Quality Assurance

<http://healthcare.partners.org/phsirb/datasafe.htm>

Adverse Event Reporting Guidelines

http://healthcare.partners.org/phsirb/adverse_events.htm

PRIVACY AND CONFIDENTIALITY

Describe methods used to protect the privacy of subjects and maintain confidentiality of data collected. This typically includes such practices as substituting codes for names and/or medical record numbers; removing face sheets or other identifiers from completed surveys/questionnaires; proper disposal of printed computer data; limited access to study data; use of password-protected computer databases; training for research staff on the importance of confidentiality of data, and storing research records in a secure location.

NOTE: Additional measures, such as obtaining a Certificate of Confidentiality, should be considered and are strongly encouraged when the research involves the collection of sensitive data, such as sexual, criminal or illegal behaviors.

All records are maintained confidential with only the investigators and technicians involved having access to the information. The subject's data will be coded by unique numbers so as to maintain both confidentiality, and blinding during data analysis. The study staff and investigators will be careful to preserve patient confidentiality under all circumstances.

With the permission of the subject, data collected that has direct clinical relevance (for example, sleep study data and blood work) will be compiled and forwarded to the relevant clinician.

SENDING SPECIMENS/DATA TO RESEARCH COLLABORATORS OUTSIDE PARTNERS

Specimens or data collected by Partners investigators will be sent to research collaborators outside Partners, indicate to whom specimens/data will be sent, what information will be sent, and whether the specimens/data will contain identifiers that could be used by the outside collaborators to link the specimens/data to individual subjects.

All procedures except circulation function testing and MRI will be conducted in Partners sites. The subject will be given a different medical record number at BIDMC and the same identifier number as being used at BWH will be used also for BIDMC testing.

De-identified skin biopsy slides will be sent to a pathology laboratory in Greece for analysis.

De-identified skin biopsy slides will be sent to a laboratory in Germany for analysis.

De-identified skin biopsy slides will be sent to a laboratory within BIDMC for analysis.

Specifically address whether specimens/data will be stored at collaborating sites outside Partners for future use not described in the protocol. Include whether subjects can withdraw their specimens/data, and how they would do so. When appropriate, submit documentation of IRB approval from the recipient institution.

The testing done at BIDMC will only be used for the purpose of this study, and will not be used for any other purpose not described in this protocol. Subjects will be allowed to withdraw their specimens or data at any time by contacting the study investigators.

RECEIVING SPECIMENS/DATA FROM RESEARCH COLLABORATORS OUTSIDE PARTNERS

When specimens or data collected by research collaborators outside Partners will be sent to Partners investigators, indicate from where the specimens/data will be obtained and whether the specimens/data will contain identifiers that could be used by Partners investigators to link the specimens/data to individual subjects. When appropriate, submit documentation of IRB approval and a copy of the IRB-approved consent form from the institution where the specimens/data were collected.

The data from testing conducted at BIDMC will be labeled with the same subject identifier as used in the tests done at BWH.

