For Aim 1 (cross-sectional study), we plan to enroll four groups of 40 subjects each: healthy controls, patients with OSA alone, patients with DM alone, and patients with DM+OSA. All four groups will be matched for age, gender, and body mass index (BMI), as well as duration of DM where appropriate.

For Aim 2 (randomized controlled trial), we plan to enroll 55 patients with DM+OSA. Data for all of these patients will be included in Aim 1, with additional data to be collected for Aim 2.

Inclusion Criteria

All patients: ≤70 years of age, weight ≤450 pounds (the maximum supported by the cardiac magnetic resonance (CMR) imaging table).

OSA patients: Respiratory disturbance index (RDI) ≥10 and <100 events/hour determined during two consecutive home sleep studies; no evidence of non-OSA sleep disorders, Epworth Sleepiness Scale (ESS) score ≤18 (/24) indicating normal/moderate daytime sleepiness levels, no history of motor vehicle accident/s or near-miss accident/s related to sleepiness within the previous two years; not a commercial driver; naïve to CPAP treatment; not currently receiving treatment of any kind for OSA.

DM patients: A clinical diagnosis of type 2 DM; glycated hemoglobin (HbA1c) <8.0% indicating stable glycemic control.

Healthy controls: Normal fasting plasma glucose (<100 mg/dl); RDI<10 events/hour determined during two consecutive home sleep studies; no evidence of any other sleep disorder/s.

Exclusion Criteria

All patients: Hematocrit <32, metallic implants or other contraindication of CMR; pregnancy; collagen vascular disease; hepatic or renal disease; cardiopulmonary disease; use of medications that could affect sleep/breathing, or that could interact with nitroglycerin, non-English speakers.

Briefly describe study procedures. Include any local site restrictions, for example, “Subjects enrolled at Partners will not participate in the pharmacokinetic portion of the study.” Describe study endpoints.

The study procedure for Aim 1 (visits 1-2) will be the same for all four subject groups (healthy controls, OSA patients, DM patients, OSA+DM patients). Patients enrolling in Aim 2 will first complete Aim 1 (visits 1-2) followed by Aim 2 (visits 3-6).

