Official Title: Vascular Impairment in Type II Diabetes Mellitus with Co-morbid Obstructive Sleep Apnea

ClinicalTrials.gov ID (NCT number): NCT01629862

Statistical Analysis Plan Date: 01/05/2018

For the cross-sectional analysis of those with diabetes, sleep apnea, both, or neither, we will first use analysis of covariance to determine whether there is any interactive effect of sleep apnea and diabetes on our primary outcome (flow mediated dilation) as well as the three secondary outcomes (nitroglycerin-induced dilation, acetylcholine-induced skin blood flow, and sodium nitroprusside-induced skin blood flow) after controlling for age, sex, and body mass index (BMI). If a significant interaction is identified, the main effects of diabetes, sleep apnea, and their interaction will be reported using multivariable linear regression adjusting for age, sex, and BMI. If the interactive effect of sleep apnea and diabetes is not significant ($\alpha=0.05$), we will ignore any interaction and examine the additive effects of diabetes and sleep apnea on each outcome using multivariable linear regression adjusting for age, sex, and BMI. Using post-hoc contrasts, we will then further test for differences between those having both diabetes and sleep apnea alone versus those with diabetes alone and those with sleep apnea alone. All tertiary outcomes will be assessed in a similar fashion.

For the randomized clinical trial analysis, the primary outcome is percent change in flow mediated dilation (post-treatment minus pre-treatment divided by pre-treatment) with percent change in nitroglycerin induced dilation, acetylcholine induced skin blood flow and sodium nitroprusside induced skin blood flow as secondary outcomes. The primary analysis will be based on the use of unpaired t-tests to compare each outcome in those randomized to CPAP versus sham-CPAP using an intention to treat principle and $\alpha =0.05$. All tertiary outcomes will be assessed in a similar fashion. If significant differences ($\alpha =0.05$) are identified in key covariates (age, sex, BMI) between those randomized to CPAP and sham CPAP, secondary analyses will adjust for those covariates that significantly differ.

For all analyses, we will also report effect sizes with 95% confidence intervals to establish the size of our effects of interest.

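### Duration of diabetes is a matching factor in Aim 1 but is absent from the SAP's models, so the DM+OSA versus DM-alone contrast has no protection against residual imbalance in it

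*Protocol*

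**What the plan says.** The protocol (Research Design and Methods, Aim 1) states that "we plan to enroll four groups of 40 subjects each". It matches all four on age, gender and BMI, "as well as duration of DM where appropriate". Only the DM-alone and DM+OSA groups have a duration, so the last factor applies to those two. No matching method or tolerance is given. For Aim 2, "we plan to enroll 55 patients with DM+OSA", and "Data for all of these patients will be included in Aim 1". The DM+OSA group in Aim 1 may therefore number 55 against 40 with DM alone.

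In the SAP's cross-sectional paragraph, the first-step analysis of covariance for the interaction controls for age, sex and BMI. The models that follow, with or without the interaction, are "multivariable linear regression adjusting for age, sex, and BMI". Post-hoc contrasts then compare DM+OSA with each single-condition group. Duration of DM does not appear in the SAP, and no paired or matched analysis is described.

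**The concern.** Three of the four matching factors are carried into the model and the fourth is dropped without a reason. Aim 1 is observational, so randomization does not balance duration. The affected contrast, DM+OSA against DM alone, is one of the two comparisons that the Aim 1 hypothesis in Specific Aims names. The same difference is one half of the interaction that the SAP tests first.

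Two consequences are possible, and they are alternatives. If the groups still differ in duration after matching, the contrast attributes part of the duration effect to sleep apnea. If matching is close, the estimate is more stable than the model recognises, and the interval is somewhat too wide. The first matters more. The protocol assigns subjects to the RDI-based groups at Visit 2, from the home sleep studies. For a diabetic patient whose sleep apnea status was unknown, the group in which duration has to be matched is therefore not known at recruitment.

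**Working it through.** The documents give no SD, target difference or power for Aim 1, so there is no figure of the plan to reproduce. The check works in SD units of the outcome given age, sex and BMI.

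**Inputs**
- From the protocol: 55 DM+OSA, and 40 in each other group.
- From the SAP: alpha 0.05 (two-sided assumed).
- Assumed: within the DM groups, duration has partial correlation r with the outcome given age, sex and BMI, with r = 0.2, 0.3 or 0.5.
- Assumed: the outcome SD is equal in all four groups.
- Assumed: residual imbalance d in duration of 0.25 or 0.5 SD; true difference for power of 0.6 SD.

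**Step 1: SAP model.** SE = sqrt(1/55 + 1/40) = 0.208. The contrast is significant when the estimate exceeds 1.96 × 0.208 = 0.407 in size.

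**Step 2: residual imbalance.** Bias = r × d. With d held fixed and no true difference, the estimate has mean r × d and spread 0.208 × sqrt(1 − r²). Example for r = 0.5, d = 0.5: mean 0.25, spread 0.180, (0.407 − 0.25)/0.180 = 0.87, which gives 19%.

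| r | Spread | Bias, d = 0.25 | Type I error | Bias, d = 0.5 | Type I error |
|---|---|---|---|---|---|
| 0.2 | 0.204 | 0.05 | 5.2% | 0.10 | 7.2% |
| 0.3 | 0.198 | 0.075 | 5.4% | 0.15 | 10.0% |
| 0.5 | 0.180 | 0.125 | 6.0% | 0.25 | 19.1% |

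If durations instead vary freely around a true mean difference of 0.25 SD, simulation at 55 versus 40 gives 5.9%, 6.8% and 9.7%. In the simulations with an imbalance and r of 0.2 to 0.5, adding duration brought the bias to about zero and kept type I error at or below 5%.

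**Step 3: close matching, d = 0.** In the pooled four-group model the residual variance is shared with subjects without DM, whom the term cannot help. DM subjects are 95/175 = 0.543 of the total. The SAP's SE divided by the SE with the term is 1/sqrt(1 − 0.543r²). The SAP's test size is 2 × P(Z > 1.96/sqrt(1 − r²)).

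| r | SE ratio, pooled | Test size, SAP | Power at 0.6 SD, SAP | Pooled model with term | Two-DM-group model with duration |
|---|---|---|---|---|---|
| 0.2 | 1.011 | 4.5% | 82.8% | 83.4% | 83.8% |
| 0.3 | 1.025 | 4.0% | 83.5% | 84.7% | 85.7% |
| 0.5 | 1.076 | 2.4% | 85.8% | 89.1% | 91.5% |

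Power is P(Z < (0.6 − 1.96 × reported SE)/spread), with the spread from Step 2. The reported SE is 0.208 for the SAP, 0.208 × sqrt(1 − 0.543r²) with the pooled term, and 0.208 × sqrt(1 − r²) in the two-group model. A simulation of the pooled model at 40/40/40/55 gave gains of 0.7, 1.4 and 3.8 points, in line with 0.6, 1.2 and 3.3 from the formula.

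**Step 4: interaction.** It equals (DM+OSA − DM) − (OSA − control), so it inherits the whole bias of Step 2. Its SE is larger, sqrt(3/40 + 1/55) = 0.305, so the effect on its error rate is smaller.

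Steps 2 and 3 take the contrast as the difference between the two groups' own adjusted means. Taken from the additive model, it would be the OSA coefficient, and the subjects without DM would dilute the bias.

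**The case against.** The strongest defence is that matching was meant to deal with duration, and that the protocol's wording is at group level. Frequency matching does not require equal numbers. A reader might infer from 55 against 40 that matching will probably be loose. The documents do not support that: unequal numbers rule out complete one-to-one pairing, but pairing is never promised, and no imbalance in duration is reported. This stands, so residual confounding is a possibility and not a finding.

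It also stands that only the partial correlation given age, sex and BMI matters. To the extent that duration tracks age, the SAP already removes part of its effect. The documents give no value, and r = 0.5, which drives the largest figures, has no support in them. Under close matching the error is conservative. The contrast is also post hoc, after the interaction test.

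A reader might further infer a gain in power from 82% to as much as 92%. That pairs a baseline without matching (0.6/0.208 gives 82%) with the precision of a model of the two DM groups only. Within close matching, and in the SAP's own pooled model, the gain is the one in Step 3.

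The defence that duration is undefined without DM does not stand. A term nested in DM is well defined, and the DM coefficient then means DM at average duration.

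**Conclusion.** The omission is plain from the two documents, and nothing else in them repairs it. Its consequences depend on duration predicting the outcome beyond age, sex and BMI; if it does not, neither effect occurs. For partial correlations of 0.2 to 0.5, the bias is 0.05 to 0.125 SD at a 0.25 SD imbalance, where type I error moves little if the imbalance is fixed. It is 0.10 to 0.25 SD at a 0.5 SD imbalance, with type I error of about 7% to 19%. Under close matching the cost is a standard error about 1% to 7.5% larger than it need be in the pooled model.

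Protection against bias is the main reason to add the term; the gain in precision is modest. A reader might infer that the Aim 1 comparison is biased or invalid as planned. The documents do not show that. This is a free improvement of low severity.

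**What to change.** Add one covariate to the Aim 1 analysis of covariance and regression models: DM × (duration of DM minus its mean among DM subjects), set to 0 for subjects without DM. Use that model for the interaction and for the DM+OSA versus DM-alone contrast. For that contrast alone, a model of the two DM groups adjusted for age, sex, BMI and duration is an alternative and recovers more precision. Report duration by group in either case.

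The cost is one SAP line and one degree of freedom, with data that matching already requires. If duration proves unrelated to the outcome, little is lost: in simulation at 40 versus 40 with r = 0, the standard error rose from 0.226 to 0.229 at a 0.25 SD imbalance and to 0.235 at 0.5 SD, that is by 1% and 4%.

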Study procedures will take place at different locations within Longwood Medical Area. In the case of inclement weather or if the subject does not wish to walk, a taxi or shuttle bus will be arranged to transport subjects. Subjects will be accompanied between sites at all times until the final procedure of each visit, apart from times when the subject will be in a hospital/clinic waiting room.

- *Visit 1: Screening Visit*

Location: BWH Ambulatory Clinical Center or BWH Clinical Trial Center

Time Required: Approximately 2.0 hours

Staff Responsible: Licensed physician, co-investigator, ACC/CTC nursing staff

All subjects will attend the BWH ACC or BWH CTC for a screening visit. Only patients who have indicated that they do not take medication/s for type 2 diabetes will be required to attend fasting. Eligibility criteria will be re-assessed verbally, and informed consent sought by a co-investigator who is not directly involved in the subject's clinical care. A licensed physician will conduct a physical examination (blood pressure, height and weight, neck, waist and hip circumference), and a thorough endocrine examination. The battery of questionnaires will then be completed. A urine sample will be obtained from females of menstrual age so that a pregnancy test can be performed; a positive result is grounds for exclusion from the study. A screening blood sample of approximately 30mL will be taken by the ACC/CTC nursing staff in order to assess exclusion criteria (plasma glucose, glycated hemoglobin, hematocrit, and eGFR). All subjects will be shown how to fill in the sleep diary, which they will complete during the seven days immediately preceding the two home sleep studies. Subjects will be given a list of foods containing a high amount of nitrates, and requested to avoid these foods during the three days immediately preceding visit 2 (and visit 6, if completing the randomized controlled trial).

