Lastly, all subjects will be given a home sleep study device and shown how to operate it. They will take this home, and when final results of screening blood samples are available, a co-investigator will contact them via telephone. Those meeting entry criteria for the study will be asked to begin the 1-week sleep diary followed by two consecutive home-based sleep studies. Visit 2 will be scheduled, and subjects will bring the sleep study device to this appointment. Those who do not meet entry criteria will be asked to return the device to the investigators (at investigators' expense).

List of questionnaires:

- Clinical Sleep Questionnaire including Epworth Sleepiness Scale;
- Short-Form 36 Health Survey;
- Pittsburgh Sleep Quality Index;

- Functional Outcomes of Sleep Questionnaire;
- Rapid Eating Assessment for Patients;
- Typical Week Physical Activity Survey;
- BIDMC Cardiac MR Center Questionnaire.

- *Visit 2: Vascular Testing, Cardiac MRI and Exercise Study*

Locations: BWH Ambulatory Clinical Center or BWH Clinical Trial Center (early morning), BIDMC Microcirculation Laboratory (mid-morning), BIDMC MRI Laboratory (late morning), BWH Shapiro Cardiovascular Center (early afternoon)

Time Required: Approximately 5 hours

Staff Responsible: Licensed physician, ACC/CTC nursing staff, MRI technician, co-investigator

Subjects will arrive at the ACC/CTC in the morning, in a fasting state. Fasting will continue until the completion of vascular testing. DM subjects will not take their short-acting insulin and/or oral hypoglycemic agents during the fasting.

Data will be downloaded from the home sleep study device using custom software. The respiratory disturbance index (RDI) will be calculated; subjects with a $RDI < 10$ will continue the study in either the DM only group or the healthy control group, and subjects with a $RDI \geq 10$ will continue the study in either the OSA only group or the DM+OSA group.

A blood sample (approximately 90mL) will be obtained by the ACC/CTC staff. 3-lead ECG will be recorded for ten minutes while seated. A non-invasive pulse wave analysis reading will be taken, which uses a small sensor placed on the wrist.

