Time Required: Approximately 5 hours

Staff Responsible: Licensed physician, ACC/CTC nursing staff, MRI technician, co-investigator

After three months of sham/active CPAP, subjects will return to the ACC or CTC in a fasting state. Adherence data will be downloaded from each device, followed by a repeat ECG measurement, questionnaires, pulse wave analysis, pregnancy testing and blood samples (approximately 90mL).

A co-investigator will accompany the subject to the BIDMC Microcirculation Laboratory for repeat vascular testing, skin biopsies, and a neuropathy evaluation.

All subjects will be provided with lunch, then accompanied to the BIDMC MRI Laboratory for a repeat cardiac MRI scan.

- *Post-Enrollment: CPAP Follow-Up*

Following Visit 6, a research assistant will access the medical record of each patient (either Beth Israel Deaconess Medical Center, or Brigham and Women's Hospital) to collect data regarding current CPAP use. If no data are found in the medical record, a research assistant will call each patient to gather this information over the phone.

The purpose of this follow-up is to investigate long-term engagement with sleep therapy following enrollment in a clinical trial. All patients who were recruited from sleep clinics were offered an appointment with their sleep specialist after study completion for ongoing sleep care. All patients who were recruited from other sources were offered a referral to a local sleep physician. We are interested in determining the rates of attendance at these clinical visits, and ascertaining whether there are differences in long-term CPAP usage by recruitment source.

For studies involving treatment or diagnosis, provide information about standard of care at Partners (e.g., BWH, MGH) and indicate how the study procedures differ from standard care. Provide information on available alternative treatments, procedures, or methods of diagnosis.

Patients with DM will already have a clinical diagnosis and will be well-established on treatment. We therefore do not suspect that we will identify any patients with undiagnosed DM. However, if this occurs, the primary care physician will be informed of the diagnosis with permission from the patient.

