The risks and benefits of the research must be fairly distributed among the populations that stand to benefit from it. No group of persons, for example, men, women, pregnant women, children, and minorities, should be categorically excluded from the research without a good scientific or ethical reason to do so. Please provide the basis for concluding that the study population is representative of the population that stands to potentially benefit from this research.

Both men and women will be recruited, although we expect that males will outnumber females in the OSA groups, due to the higher prevalence of OSA amongst males.

We expect the proportion of minorities to represent those in the New England area. All potentially eligible subjects will be considered for inclusion regardless of race, ethnicity, or nationality.

The risk factors for OSA are different between children and adults, and CPAP is not the first-line treatment for OSA in children. Individuals under 18 years of age will therefore be excluded. The difference in endothelial

function between OSA patients and controls is not obvious beyond the age of 50; we will ensure that a range of ages are recruited to investigate this further.

Finally, OSA can occur during pregnancy due to other risk factors occurring during this period, and there is also a paucity of safety data concerning the vascular measurements undertaken during pregnancy. We therefore plan to exclude pregnant women.

When people who do not speak English are excluded from participation in the research, provide the scientific rationale for doing so. Individuals who do not speak English should not be denied participation in research simply because it is inconvenient to translate the consent form in different languages and to have an interpreter present.

Subjects who do not speak English will be excluded, as the battery of questionnaires is in English. These have not been validated for use in other languages.

For guidance, refer to the following Partners policy:

Obtaining and Documenting Informed Consent of Subjects who do not Speak English
<http://healthcare.partners.org/phsirb/nonengco.htm>

RECRUITMENT PROCEDURES

Explain in detail the specific methodology that will be used to recruit subjects. Specifically address how, when, where and by whom subjects will be identified and approached about participation. Include any specific recruitment methods used to enhance recruitment of women and minorities.

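### The only pregnancy test described before the first vascular measurements is at Visit 1, at least 9 days earlier; Visit 2 lists none, while Visit 6 tests on the day

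*Protocol*

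**What the plan says.** Pregnancy is an exclusion for all subjects (Protocol, Exclusion Criteria). Equitable Selection of Subjects gives two reasons. One is that sleep apnea in pregnancy can arise from other risk factors. The other is a "paucity of safety data concerning the vascular measurements undertaken during pregnancy".

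The test is placed at the screening visit (Protocol, Visit 1): "A urine sample will be obtained from females of menstrual age so that a pregnancy test can be performed". A positive result excludes the woman.

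Several steps then separate Visit 1 from Visit 2. The subject takes the sleep-study device home and waits: "when final results of screening blood samples are available, a co-investigator will contact them via telephone". After the call, "Those meeting entry criteria for the study will be asked to begin the 1-week sleep diary followed by two consecutive home-based sleep studies". The device is brought back at Visit 2.

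Visit 2 is where the vascular measurements are first made. Its description covers fasting, the device download, blood sampling, ECG, pulse wave analysis, brachial artery testing with nitroglycerin, skin blood flow with acetylcholine and sodium nitroprusside, skin biopsies, a neuropathy evaluation in diabetic patients, cardiac MRI and optional exercise. No pregnancy test appears.

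Visit 6, at the end of the randomized trial, repeats the vascular testing, biopsies, neuropathy evaluation and MRI. Among the tasks on arrival that day it lists "pregnancy testing and blood samples (approximately 90mL". The SAP does not touch on this point.

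**The concern.** One of the two stated reasons for the pregnancy exclusion is tied to particular procedures, so the status that matters is the woman's status on the day of those procedures. At Visit 6 the protocol establishes that status on the day. At Visit 2 it relies on a result that is at least 9 days old and has no upper limit on its age.

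If the visits are run as written, a woman who conceives after screening, or whose pregnancy was too early to detect at Visit 1, goes through Visit 2 as eligible. The exclusion is then formally met at screening but not at the exposure it is partly meant to prevent. The stake is subject safety and the working of an exclusion that the protocol already contains. The effect on the statistical analysis would be negligible.

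**Working it through.** The protocol states no interval between Visit 1 and Visit 2, so there is no figure of its own to reproduce. The lower bound follows from the order of events.

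**Inputs**
- Wait from Visit 1 to the telephone call and start of the diary: w days, w ≥ 0, length not stated (Visit 1, closing paragraph).
- Sleep diary: 7 days, "which they will complete during the seven days immediately preceding the two home sleep studies" (Visit 1).
- Home sleep studies: 2 successive nights, after the diary (Visit 1, closing paragraph).
- Visit 2 comes after the studies, because the device is returned and its data downloaded there.

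**Formula**

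Test-to-exposure gap at Visit 2 ≥ w + 7 + 2 = w + 9 days, plus any scheduling delay.

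| Assumed w (days) | Minimum gap (days) |
|---|---|
| 0 | 0 + 7 + 2 = 9 |
| 1 | 1 + 7 + 2 = 10 |
| 3 | 3 + 7 + 2 = 12 |
| 7 | 7 + 7 + 2 = 16 |

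Only the first row is a bound set by the document. The others are assumptions that show how the wait for results moves it. No maximum is stated.

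**Side by side**

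| | Visit 2 | Visit 6 |
|---|---|---|
| Nitroglycerin, acetylcholine and nitroprusside testing | yes | yes, repeated |
| Cardiac MRI | yes | yes, repeated |
| Pregnancy test listed that day | no | yes, among the arrival tasks |
| Age of most recent listed test | at least 9 days | 0 days |

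**Who relies on the Visit 1 test alone**

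Everyone attends Visit 2. The three groups in Aim 1 only (healthy controls, diabetes alone, sleep apnea alone; 3 × 40 = 120 planned) finish there, so for them the Visit 6 test never happens. Subjects who go on to Aim 2 do reach it, but only after they have already been through Visit 2. The 120 is a count of planned subjects of both sexes. The documents do not give the number of women of menstrual age, so no number at risk can be derived.

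**The case against.** The best defence is that Visit 6 does not set a same-day standard. Its list of arrival tasks combines items from Visit 1 (questionnaires, pregnancy test) with items from Visit 2 (ECG, pulse wave analysis). The test there can be read as the counterpart of the screening test, needed because about 9 + 7 + 91 = 107 days or more have passed since Visit 1 (minimum gap to Visit 2, titration week, three months of treatment; run-in not counted) and there is no second screening visit. One test per testing episode is a coherent design, and no section says how recent a negative result must be. This stands, and it is why the point is an inconsistency in safeguards and not a contradiction. It does not close the Visit 2 gap.

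The likely harm should not be overstated either. The protocol cites a lack of safety data, not known harm. Foreseeable Risks and Discomforts reports no known risks of cardiac MRI. Ages run up to 70, and men are expected to outnumber women in the sleep apnea groups. This also stands.

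Three stronger readings are tempting, and the documents do not support them.

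- *Medication has the same gap.* The protocol also excludes "use of medications that could affect sleep/breathing, or that could interact with nitroglycerin", and the only check described is at Visit 1: "Eligibility criteria will be re-assessed verbally". A reader might infer that nobody asks again before nitroglycerin is given. That is an argument from silence. The exclusion carries no time limit, a licensed physician gives the drug and monitors the subject afterwards, and the form asks only for a brief description of procedures. Nor is there a Visit 6 re-check to contrast with, as there is for pregnancy.
- *Visits 2 and 6 are identical exposure days.* They share the vascular tests, biopsies and MRI, but the Visit 6 procedures describe no exercise test. The stated safety reason covers the vascular measurements, not every procedure of the day.
- *All 160 to 175 Aim 1 subjects are at risk* (4 × 40, or 3 × 40 + 55). That counts everyone who attends Visit 2, men included, and does not measure pregnancy risk.

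**Conclusion.** The point holds for pregnancy. As written, the exclusion is verified at Visit 1 and not again before the first of the measurements that partly motivate it, at least 9 days later and with no stated limit. The same protocol lists a test on the day when those measurements are repeated at Visit 6.

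The 9 days is a lower bound derived from the schedule. It assumes that the diary starts without delay and that Visit 2 falls the morning after the second sleep study. The contrast with Visit 6 assumes that the order in which its tasks are listed is the order in which they are done. The number of women affected cannot be estimated from the documents and is probably small. The case for change therefore rests on the low cost of closing the gap, not on a demonstrated frequency of harm.

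**What to change.** Reconcile Visit 1, Visit 2, Visit 6 and Equitable Selection of Subjects so that the pregnancy exclusion is verified at Visit 2 on the same basis the protocol already uses at Visit 6. Keep the Visit 1 test: relocating it would let a pregnant woman go through the screening blood draw, diary and sleep studies before being excluded. The clinical rule itself, including how recent a result must be, is for the investigators to decide and state.

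The cost is a short amendment and about one urine test per woman of menstrual age at Visit 2, with no added visit or staff. The downside is an occasional exclusion at Visit 2, after the subject has completed the diary and sleep studies.
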